2.1.5. Clinical Safety of Encorafenib

The maximum well-tolerated dose of encorafenib when given as a single agent is 300 mg QD. Encorafenib 300 mg QD as a single agent is associated with an increased risk of certain AEs compared to when used in combination with binimetinib. For example, Grade 3 or 4 dermatologic reactions in the COLUMBUS study occurred in 21% of patients treated with single-agent encorafenib compared to 2% of patients treated with encorafenib in combination with binimetinib.

Among patients receiving single-agent encorafenib 300 mg QD across multiple clinical trials including COLUMBUS, the most common AEs ($\geq 20\%$, all grades) were alopecia (50%), palmar-plantar erythrodysesthesia syndrome (48%), arthralgia (43%), hyperkeratosis (42%), nausea (35%), dry skin (29%), fatigue (28%), myalgia (28%), headache (27%), vomiting (25%), rash (23%) and palmoplantar keratoderma (22%).

Encorafenib is primarily metabolized and eliminated by the liver; patients with mild to severe hepatic impairment may have increased exposure over the range of inter-patient variability exposure.

Detailed information regarding clinical safety of encorafenib used as a single agent is presented in the encorafenib Investigator's Brochure.

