2.2. Benefit/Risk Assessment

Data from the COLUMBUS study and preclinical and exposure-response data for encorafenib and binimetinib demonstrate that both agents in combination contribute to observed efficacy (Dummer et al, 2018a; Dummer et al, 2018b). Co-administration of encorafenib 450 mg QD with binimetinib 45 mg BID reduces the incidence of safety findings of interest for binimetinib (acneiform dermatitis, peripheral edema and rash) and encorafenib (arthralgia, myalgia, vomiting, headache, rash and palmoplantar keratoderma). The reduction of encorafenib toxicity with the addition of binimetinib enables a higher dose of encorafenib, as well as fewer dose interruptions and reductions, which may enhance the efficacy of the combination.

The primary risks of the combination of encorafenib plus binimetinib treatment are well characterized and include known class effects of BRAF and MEK inhibitors (see Sections 2.1.4 and 2.1.5). The combination of encorafenib plus binimetinib has a lower frequency and severity of pyrexia and photosensitivity reactions than the dabrafenib plus trametinib and vemurafenib plus cobimetinib combinations, respectively. Pyrexia was infrequent with the combination of encorafenib plus binimetinib, not complicated by chills,

dehydration or renal failure and generally not recurrent. Almost all cases of pyrexia presenting as an SAE were associated with secondary causes of infection of progressive melanoma. Photosensitivity was infrequent (4.7%) in the encorafenib 450 mg QD plus binimetinib 45 mg BID arm of the COLUMBUS study.

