6.6. Dose Modification

6.6.1. Dose Interruptions

Following initiation of therapy, treatment with encorafenib and binimetinib may be delayed to allow resolution of toxicity. Patients may resume treatment if no medical condition or other circumstance exists that, in the opinion of the Investigator, would make the patient unsuitable for further participation in the study.

Individual decisions regarding dose interruptions and modifications should be made using appropriate clinical judgment, considering relatedness of the AE to the study treatment and the patient's underlying condition. Adverse events that have a clear alternative explanation, or transient (\leq 72 hours) abnormal laboratory values without associated clinically significant signs or symptoms may be exempt from dose-reduction rules. The treating Investigator

should refer to and follow the labeled guidance and/or institutional guidelines for the management of toxicities relating to encorafenib and binimetinib. Detailed guidelines can also be found in Appendix 2 and Appendix 3.

Dose interruptions are permitted in the case of medical/surgical events or logistical reasons not related to study treatment (e.g., elective surgery, unrelated medical events, vacation, holidays). Patients should be placed back on study treatment within 2 weeks (14 days) of the scheduled interruption, unless otherwise discussed with the Sponsor. The reason for interruption will be documented in the patient's study record.

If a patient misses > 6 weeks (i.e., 42 consecutive days) of dosing with encorafenib, study treatment with encorafenib will be permanently discontinued. Due to the potential for limited efficacy of binimetinib alone in the study population, if a patient permanently discontinues treatment with encorafenib, they must also permanently discontinue treatment with binimetinib.

If a patient misses > 6 weeks (i.e., 42 consecutive days) of dosing with binimetinib, study treatment with binimetinib will be permanently discontinued. If a patient discontinues treatment with binimetinib, the patient may continue treatment with encorafenib. Due to the potential for increased toxicity when binimetinib is discontinued, doses of single-agent encorafenib may need to be decreased.

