12. APPENDIX 2: RECOMMENDED DOSE MODIFICATIONS FOR ENCORAFENIB-RELATED* ADVERSE EVENTS

| Severity of Adverse Event | Dose Modifications | |
|--|--|--|
| New Primary Malignancies | | |
| Non-cutaneous RAS mutation-positive malignancies | Permanently discontinue encorafenib and binimetinib. | |
| Uveitis | | |
| Grade 1-3 | If Grade 1 or 2 does not respond to specific ocular therapy, or for Grade 3 uveitis, withhold encorafenib and binimetinib for up to 6 weeks. | |
| | If improved, resume at same or reduced dose. If not improved, permanently discontinue. | |
| Grade 4 | Permanently discontinue encorafenib and binimetinib. | |
| Other Eye Disorders (i.e., non-Uveitis Events) | | |
| Grade 1–2 | Maintain dose level of encorafenib and binimetinib and increase frequency of ophthalmic monitoring to at least every 14 days until stabilization or resolution. | |
| Grade 3 | Interrupt dosing of encorafenib and binimetinib and refer patient to ophthalmologist within 7 days. | |
| | If resolved to Grade ≤ 1 in ≤ 21 days, resume treatment at 1 reduced dose level of encorafenib and binimetinib. | |
| | If not resolved to Grade ≤ 1 in ≤ 21 days, permanently discontinue encorafenib and binimetinib and close follow-up with ophthalmic monitoring until stabilization or resolution. | |
| Grade 4 | Permanently discontinue encorafenib and binimetinib and immediate follow-up with ophthalmic monitoring until stabilization or resolution. | |
| QTc Prolongation | | |
| $QTcF > 500 \text{ ms and} \le 60 \text{ ms increase from baseline}$ | 1 st occurrence: | |
| | • Temporarily interrupt dosing of encorafenib until QTcF < 500 ms. Then resume treatment at 1 reduced dose level of encorafenib. | |
| | 2 nd occurrence: | |

| Severity of Adverse Event | Dose Modifications | |
|---|--|--|
| | • Temporarily interrupt dosing of encorafenib treatment until QTcF < 500 ms. Then resume treatment at 1 reduced dose level of encorafenib. | |
| | Permanently discontinue encorafenib and binimetinib. | |
| QTcF > 500 ms and > 60 ms increase from baseline | Permanently discontinue encorafenib and binimetinib. | |
| Hepatotoxicity | | |
| Grade 2 AST or ALT increased | Maintain encorafenib dose. | |
| | • If no improvement within 4 weeks, withhold encorafenib until improved to Grade 0-1 or to pretreatment/baseline levels and then resume at the same dose. | |
| Grade 3 or 4 AST or ALT increased | See Other Adverse Reactions | |

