13. APPENDIX 3: RECOMMENDED DOSE MODIFICATIONS FOR BINIMETINIB-RELATED* ADVERSE EVENTS

| Severity of Adverse Event | Dose Modifications | | |
|--|--|--|--|
| Cardiomyopathy | | | |
| Asymptomatic, absolute decrease in LVEF of $> 10\%$ from baseline that is also below the LLN | Withhold binimetinib for up to 4 weeks, evaluate LVEF every 2 weeks. | | |
| | Resume binimetinib at a reduced dose if the following are present: | | |
| | LVEF is at or above the LLN and Absolute decrease from baseline is 10% or less and Patient is asymptomatic. If LVEF does not recover within 4 weeks | | |
| | permanently discontinue binimetinib. | | |
| Grade 3-4 (Symptomatic congestive heart failure or absolute decrease in LVEF of $> 20\%$ from baseline that is also below LLN) | Permanently discontinue binimetinib. Closely monitor LVEF until resolution or up to 16 weeks. | | |
| Venous Thromboembolism | | | |
| Uncomplicated DVT or PE | Withhold binimetinib. | | |
| | If improves to Grade 0-1, resume at a reduced dose. If no improvement, permanently discontinue binimetinib. | | |
| Life threatening PE | Permanently discontinue binimetinib. | | |
| Serous Retinopathy | | | |
| Symptomatic serous retinopathy/ Retinal pigment epithelial detachments | Withhold binimetinib for up to 10 days. If improves and becomes asymptomatic, resume at the same dose. If not improved, resume at a lower dose level or permanently discontinue binimetinib. | | |
| Retinal Vein Occlusion (RVO) | | | |
| Any Grade | Permanently discontinue binimetinib. | | |
| Uveitis | | | |
| Grade 1-3 | If Grade 1 or 2 does not respond to specific ocular therapy, or for Grade 3 uveitis, withhold binimetinib and encorafenib for up to 6 weeks. | | |
| | If improved, resume at same or reduced dose. If not improved, permanently discontinue binimetinib. | | |
| Grade 4 | Permanently discontinue binimetinib. | | |

| Severity of Adverse Event | Dose Modifications | |
|---|--|--|
| Other Eye Disorders (i.e., Non-retinal Events, non-Uveitis Events | | |
| Grade 1-2 | Maintain dose level of encorafenib and binimetinib and increase frequency of ophthalmic monitoring to at least every 14 days until stabilization or resolution. | |
| Grade 3 | Interrupt dosing of encorafenib and binimetinib and refer patient to ophthalmologist within 7 days. | |
| | • If resolved to Grade ≤ 1 in ≤ 21 days, resume treatment at 1 reduced dose level of encorafenib and binimetinib. | |

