| | • If not resolved to Grade ≤ 1 in ≤ 21 days, permanently discontinue encorafenib and binimetinib and close follow-up with ophthalmic monitoring until stabilization or resolution. | |
| Grade 4 | Permanently discontinue encorafenib and binimetinib and immediate follow-up with ophthalmic monitoring until stabilization or resolution. | |
| Interstitial Lung Disease | | |
| Grade 2 | Withhold binimetinib for up to 4 weeks. | |
| | If improved to Grade 0-1, resume at a reduced dose. If not resolved within 4 weeks, permanently discontinue. | |
| Grade 3 or Grade 4 | Permanently discontinue binimetinib. | |
| Hepatotoxicity | | |
| Grade 2 AST or ALT increased | Maintain binimetinib dose. | |
| | • If no improvement within 2 weeks, withhold binimetinib until improved to Grade 0-1 or to pretreatment/baseline levels and then resume at the same dose. | |
| Grade 3 or 4 AST or ALT increased | See Other Adverse Reactions. | |
| Rhabdomyolysis or Creatine Phosphokinase (CPK) elevations | | |
| Grade 4 asymptomatic CPK elevation or | Withhold binimetinib dose for up to 4 weeks. | |
| Any Grade CPK elevation with symptoms or with renal impairment | If improved to Grade 0-1 resume at a reduced dose. If not resolved within 4 weeks, permanently discontinue binimetinib. | |

| Severity of Adverse Event | Dose Modifications | |
|---|--|--|
| Dermatologic | | |
| Grade 2 | If no improvement within 2 weeks, withhold until Grade 0-1. Resume at same dose if first occurrence or reduce dose if recurrent. | |
| Grade 3 | Withhold until Grade 0-1. Resume at same dose if first occurrence or reduce dose if recurrent. | |
| Grade 4 | Permanently discontinue binimetinib and encorafenib. | |
| Nausea/Vomiting | | |
| Grade 1-2 | Maintain dose level of encorafenib and binimetinib. Promptly institute antiemetic measure. | |
| Grade 3 | Interrupt dosing of encorafenib and binimetinib until resolved to Grade ≤ 1 . Then resume treatment at 1 reduced dose level of encorafenib. Resume treatment with binimetinib at the current dose if, in the judgment of the Investigator, the toxicity is considered to be unrelated to binimetinib, or at 1 reduced dose level. Note: Interrupt dosing of encorafenib and binimetinib for \geq Grade 3 vomiting or Grade 3 nausea only if the vomiting or nausea cannot be controlled with optimal antiemetics (as per local practice). If unresolved permanently discontinue binimetinib and encorafenib. | |
| Grade 4 | Permanently discontinue binimetinib and encorafenib. | |

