| Other Adverse Reactions | | |
| Recurrent Grade 2 or First occurrence of any Grade 3 | Withhold for up to 4 weeks. If improves to Grade 0-1 or to pretreatment/baseline levels, resume at reduced dose. If no improvement, permanently discontinue binimetinib and encorafenib. | |
| First occurrence of any Grade 4 | Permanently discontinue or withhold for up to 4 weeks. If improves to Grade 0-1 or to pretreatment/baseline levels, then resume a reduced dose. If no improvement, permanently discontinue binimetinib and encorafenib. Consider permanently discontinuing binimetinib at | |
| | encorafenib. | |

| Severity of Adverse Event | Dose Modifications |
|---------------------------|--|
| Recurrent Grade 4 | Permanently discontinue binimetinib and encorafenib. |

*For adverse events that may be related to both binimetinib and encorafenib, guidance is provided for the other agent also.

14. APPENDIX 4: ADVERSE EVENTS: DEFINITIONS AND PROCEDURES FOR RECORDING, EVALUATING, FOLLOW-UP, AND REPORTING

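### Protocol Section 6.6.1 states no encorafenib ceiling when binimetinib alone is stopped or held, so a patient can remain on 450 mg QD, 1.5 times the stated single-agent tolerable dose, unless guidance outside the protocol limits it

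*Protocol*

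**What the plan says.** All references are to the protocol.

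- **Starting dose (Section 4.3, Table 6).** Encorafenib 450 mg QD with binimetinib 45 mg BID.
- **Single-agent tolerability (Section 2.1.5).** "The maximum well-tolerated dose of encorafenib when given as a single agent is 300 mg QD".
- **Why 450 mg is usable (Section 2.2).** "The reduction of encorafenib toxicity with the addition of binimetinib enables a higher dose of encorafenib".
- **Stopping one drug (Section 6.6.1).** More than 42 consecutive days without binimetinib means it is permanently stopped. Encorafenib may then go on alone. The section recognises that toxicity may rise and adds that "doses of single-agent encorafenib may need to be decreased". That sentence concerns discontinuation; the section gives no encorafenib dose for a temporary binimetinib hold. The reverse case is binding: if encorafenib stops, binimetinib must stop too.
- **Dose levels (Section 6.6.2, Table 7).** The two drugs are reduced independently. Encorafenib levels are 450, 300 and 225 mg QD, and none is tied to whether binimetinib is being taken.
- **Appendix 3 footnote.** "For adverse events that may be related to both binimetinib and encorafenib, guidance is provided for the other agent also". Several rows nevertheless act on binimetinib only, for example the asymptomatic LVEF row: "Withhold binimetinib for up to 4 weeks, evaluate LVEF every 2 weeks".
- **Grade 2 AST/ALT.** Appendix 2 says "Maintain encorafenib dose" and then "If no improvement within 4 weeks, withhold encorafenib until improved to Grade 0-1". Appendix 3 says "If no improvement within 2 weeks, withhold binimetinib until improved to Grade 0-1".

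**The concern.** The protocol gives a tolerability limit for encorafenib alone and explains that binimetinib is what allows a higher dose. It then foresees patients losing binimetinib and does not require the dose to come down. Elsewhere it writes firm rules: Section 6.5.1.1 halves encorafenib when a moderate CYP3A4 inhibitor cannot be avoided, and Section 6.6.2 bars re-escalation after named toxicities. Losing the drug that makes 450 mg tolerable gets only a permissive sentence, and a binimetinib-only hold gets none.

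What is at stake is the safety of individual patients. The primary analysis is not involved.

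**Working it through.** No sample-size or power figure is involved, so the check is a reading of the dosing text plus simple arithmetic.

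**1. Size of the gap.** 450 / 300 = 1.5, and 450 − 300 = 150 mg per day above the Section 2.1.5 figure. A patient already at 300 or 225 mg is not above it.

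**2. Appendix 3 rows that act on binimetinib alone.** None of these carries an encorafenib instruction.

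| Event | Binimetinib action |
|---|---|
| Grade 3-4 cardiomyopathy | Permanent stop |
| RVO, any grade | Permanent stop |
| ILD, Grade 3-4 | Permanent stop |
| Asymptomatic LVEF decrease | Hold up to 4 weeks |
| ILD, Grade 2 | Hold up to 4 weeks |
| CPK elevation meeting the row's criteria | Hold up to 4 weeks |
| Uncomplicated DVT/PE | Hold, no limit in the row (42 days under Section 6.6.1) |
| Symptomatic serous retinopathy | Hold up to 10 days |
| Grade 2 AST/ALT | Hold after 2 weeks without improvement |

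**3. The AST/ALT stagger.** Suppose Grade 2 AST/ALT elevation does not improve and both appendices are followed. Binimetinib is held from week 2 and encorafenib is maintained until week 4. For those 14 days, the two instructions taken together produce single-agent encorafenib at whatever dose the patient was taking.

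**4. Excess over 300 mg QD for a patient on 450 mg.**
- 14-day AST/ALT interval: 150 × 14 = 2,100 mg.
- 28-day hold: 150 × 28 = 4,200 mg.
- 42-day hold: 150 × 42 = 6,300 mg.
- After a permanent binimetinib stop, there is no end date until another criterion applies.

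These are dose totals. The documents do not link them to a toxicity rate.

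**5. How many patients.** Assume that the melanoma rates in Section 2.1.4 carry over to the 107 patients expected.
- Permanent stops: Grade 3 left ventricular dysfunction at 1.6% gives 107 × 0.016 = 1.7. Adding RVO (0.1%) and pneumonitis (0.3%) gives 107 × 0.020 = 2.1. The second figure overcounts, because Grade 2 ILD is first held.
- Longer holds: ejection-fraction decrease other than Grade 3 is 7% − 1.6% = 5.4%, or 107 × 0.054 = 5.8. Venous thromboembolism at 6% gives 107 × 0.06 = 6.4. The total is 6.4 with full overlap and 5.8 + 6.4 = 12.2 with none.

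The hold figures assume that every event meets the hold trigger in a patient on 450 mg, and they include events that other rules would catch. CPK, ILD and AST/ALT holds are not counted. The range is illustrative; neither end is a bound.

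**6. What other text could lower the dose.**
- Appendix 2 acts on encorafenib for dermatologic and hand-foot reactions, QTcF prolongation, Grade 3 eye events, and recurrent Grade 2 or first Grade 3 other reactions. It covers encorafenib-related events and responds after they occur.
- Section 6.7 stops all treatment for Grade 4 or life-threatening events unless the Sponsor approves otherwise, and for a related event when the Investigator judges that continuing is against the patient's interest.
- Section 6.7 also lists more than six weeks of missed dosing, but by reference to Section 6.6.1, which keeps encorafenib available when only binimetinib was missed.

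None of these lowers encorafenib because binimetinib has gone. A Grade 3 LVEF decrease attributed to binimetinib alone stops binimetinib and leaves encorafenib at 450 mg unless the Investigator chooses otherwise.

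**The case against.** **Label or institutional guidance may already set the limit.** Sections 6.6.1 and 6.6.2 direct the Investigator to one or both of these, and the appendices are titled as recommendations. This stands in part. The guidance is not in the documents, so one cannot conclude that patients will in practice be kept on 450 mg alone, which a reader might infer. But the pointer can be met by institutional guidance alone, so it is not a ceiling stated in the protocol.

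**Section 6.6.1 already names the hazard and leaves the dose to clinical judgement.** True for permanent discontinuation. Judgement may lower the dose, but nothing requires it, and the sentence does not reach holds.

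**Single-agent toxicity is not unmanaged.** Correct. The Appendix 2 rows and Section 6.7 apply, and under Section 9.6.1 the Sponsor and a Steering Committee monitor safety. These respond to toxicity; they do not prevent dosing above the tolerability figure.

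**The dermatologic contrast in Section 2.1.5 does not measure the gap.** Also correct. The 21% versus 2% for Grade 3-4 reactions compares single-agent encorafenib, given at 300 mg in that study, with the combination. A reader might take 21% as the risk that a cap would remove. It is the rate at the proposed cap, under single-agent treatment rather than a hold of a few weeks.

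**A cap could strand patients at 300 mg.** Section 6.6.2 ties re-escalation to resolution of the adverse event that caused the reduction. A cut made only because binimetinib was held has no such event, so the fix needs its own route back.

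**Conclusion.** The concern holds as a gap in the protocol's dosing text. Unless guidance outside the documents sets a limit, a compliant patient who loses binimetinib can stay on 450 mg QD encorafenib, 1.5 times the protocol's own single-agent figure. It is clearest for permanent binimetinib-only stops, such as a Grade 3 LVEF decrease or RVO, and for the two-week AST/ALT stagger. It is narrower for events also judged encorafenib-related, where Appendix 2 often acts.

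The size of the harm is unknown, because the documents give no toxicity rate for 450 mg alone. The number affected is probably small: about two permanent stops among 107 patients if the melanoma rates carry over, plus some holds.

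A reader might also infer that the trial's efficacy conclusion is affected. The documents do not support that: the ORR hypotheses, alpha, power and sample size do not depend on this rule. The change is still worth making, because it is inexpensive and the protocol's own background supplies the reason for it.

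**What to change.** - **Section 6.6.1.** Replace the permissive sentence with a rule. Encorafenib is to be no more than 300 mg QD (Table 7 level -1) once binimetinib is permanently discontinued, and during any binimetinib-only hold longer than a short duration set by the sponsor. That duration is a judgement; the 10 days allowed for serous retinopathy is one possible reference. Patients at 300 or 225 mg need no further cut.
- **Section 6.6.2.** State that encorafenib reduced solely for this reason may return to its prior dose when binimetinib resumes, without the 14-day adverse-event condition, if no encorafenib toxicity prevents it.
- **Appendices.** Cross-reference the rule in the binimetinib-only rows of Appendix 3 and the Grade 2 AST/ALT row of Appendix 2.

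The cost is text in four places, with no added visits, procedures or patients. The downside is lower encorafenib exposure in the few patients who would have tolerated 450 mg alone.

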6.6.2. Dose Modifications

Doses of encorafenib and binimetinib may be independently reduced for toxicity management as outlined in Table 7 and Table 8, respectively. All dose modifications are based on the worst preceding toxicity. The treating Investigator should refer to and follow the labeled guidance and/or institutional guidelines for the management of toxicities relating to encorafenib and binimetinib. Detailed guidelines can also be found in Appendix 2 and Appendix 3.

When the AE that resulted in a dose reduction improves to and remains stable to the patient's baseline for a minimum of 14 days, the dose can be re-escalated to the next higher dose level at the discretion of the Investigator, provided there are no other concomitant toxicities that would prevent drug re-escalation. There is no limit to the number of times the patient can have their dose reduced or re escalated; however:

- No dose re-escalation of encorafenib is allowed after a dose reduction due to prolonged $QTcF \ge 501$ msec
- No dose re-escalation of binimetinib is allowed after a dose reduction due to LVEF dysfunction
- No dose re-escalation of binimetinib or encorafenib is allowed after a dose reduction due to ocular toxicity ≥ Grade 2

| Dose Level | Encorafenib |
|-------------------|------------------------|
| 0 (starting dose) | 450 mg QD |
| -1 | 300 mg QD |
| -2 | 225 mg ^a QD |

| Table 7. | Dose | Reductions | for | Encorafenib |
|----------|------|------------|-----|-------------|
|----------|------|------------|-----|-------------|

NOTE: Dose reduction should be based on the highest AE grade.

a Dose reduction below 225 mg QD of encorafenib is not allowed.

Table 8. **Dose Reductions for Binimetinib**

| Dose Level | Binimetinib |
|-------------------|------------------------|
| 0 (starting dose) | 45 mg BID |
| -1 | 30 mg ^a BID |

NOTE: Dose reduction should be based on the highest AE grade.

a Dose reduction below 30 mg BID of binimetinib is not allowed.

